### **Lymphoma –NHL combination therapy (Cohort 5)**

Approximately 30-66 subjects will be evaluated in this cohort, depending on the number of dose levels of lenalidomide assessed during safety run-in. Subjects in the safety run-in treated at the RP2D will be included in the dose expansion evaluation of 30 subjects for efficacy (see Section 5.2.1.3 for details).

The maximum half-width of the 2-sided 90% exact CI will be 16% with a targeted number of 30 subjects. [Table 19](#) describes examples of 90% CIs across a possible range of ORRs.

Table 19      Precision (90% Confidence Intervals) for range of observed ORR (33% - 83%)

Number of responses/Number of treated subjects (ORR)	90% 2-sided Confidence Interval*
10/30 (33%)	(19, 50)
15/30 (50%)	(34, 66)
20/30 (67%)	(50, 81)
25/30 (83%)	(68, 93)

\*exact (Clopper-Pearson) confidence limit for the binomial proportion

#### **8.2.8 Subgroup Analyses and Effect of Baseline Factors**

No other subgroup analysis is planned.

#### **8.2.9 Interim Analyses**

Unless otherwise indicated, an interim analysis will be performed if fewer than 10 subjects are enrolled in a cohort 6 months after the time that the first subject is treated in the respective cohort. The interim analysis will take place after 10 subjects have reached the Week 12 assessment. Results will be reviewed by the study team.

### **MDS/HL (Cohorts 1 and 3)**

For the MDS and HL cohorts, if an interim analysis is conducted and 1 or fewer subjects out of the first 10 subjects with a post-baseline (Week 12) assessment/imaging scan have a confirmed or unconfirmed primary endpoint response (OR or CR respectively), then enrollment will be paused until response data for the subsequent (Week 24) assessment/imaging scan are reviewed for all subjects already enrolled in the trial (including those enrolled who have not reached the first post-baseline assessment/imaging scan). Enrollment will be resumed if the observed responses (confirmed or unconfirmed) for the primary endpoint in the respective cohort among subjects who are still enrolled in the trial indicates that the probability of the response for the primary endpoint >10% is at least 80%

(e.g.,  $\geq 3/16$  confirmed or unconfirmed responses). See Section 12.8 for further details regarding the decision rules for resuming enrollment following the interim analysis. If the required number of responses is observed, enrollment will be resumed in the respective cohort regardless of whether all subjects have had disease assessments through Week 24. [Table 20](#) provides the operating characteristics for the interim analysis rule in MDS and HL.

Table 20 Operating Characteristics of Interim Analysis Rule for MDS and HL – Pause Enrollment if  $\leq 1/10$  Subjects Achieve an Overall Response (MDS) or a Complete Response (HL); Final Analysis with 25 Subjects

True ORR	Probability of Pausing Enrollment	Probability of Passing the IA and Achieving Study Success
10%	0.73	0.03
15%	0.54	0.14
20%	0.37	0.34
25%	0.25	0.55
30%	0.15	0.74
35%	0.09	0.87
40%	0.05	0.93

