### **MM (Cohort 2) and NHL (Cohorts 4A and 4B)**

For the MM (Cohort 2) and combined MLBCL and PD-L1 positive NHL Cohorts 4A and 4B, respectively), if an interim analysis is conducted and 3 or fewer subjects out of the first 10 subjects with a post-baseline (Week 12) imaging scan have a confirmed or unconfirmed primary endpoint response, then enrollment will be paused until response data for the subsequent imaging scan (Week 24) are reviewed for all subjects already enrolled in the trial (including those enrolled who have not reached the first post-baseline scan). Enrollment will be resumed if the observed responses (confirmed or unconfirmed) for the primary endpoint in the respective cohort among subjects who are still enrolled in the trial indicates that the probability of the response for the primary endpoint  $>25\%$  is at least 80% (e.g.,  $\geq 5/16$  confirmed or unconfirmed responses). See Section 12.8 for further details regarding the decision rules for resuming enrollment following the interim analysis. If the required number of responses is observed, enrollment will be resumed in the respective cohort regardless of whether all subjects have had disease assessments through Week 24. [Table 21](#) provides the operating characteristics for this interim analysis rule in MM and MLBCL and PD-L1 Positive NHL Cohorts, respectively.

No interim analysis is planned for subjects with unselected PD-L1 status with relapsed / refractory FL (Cohort 4C) or DLBCL (Cohort 4D).

Table 21 Operating Characteristics of Interim Analysis Rule for MLBCL and PD-L1 Positive NHL subjects (Cohorts 4A and 4B) and MM (Cohort 1)– Pause Enrollment if  $\leq 3/10$  Subjects Achieve an Overall Response (PR or better); Final Analysis with 28 Subjects

True ORR	Probability of Pausing Enrollment	Probability of Passing the IA and Achieving Study Success
25%	0.78	0.02
30%	0.65	0.08
35%	0.51	0.20
40%	0.38	0.37
45%	0.27	0.57
50%	0.17	0.74
55%	0.10	0.86
60%	0.05	0.93

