## 12.8 Interim Analysis Decision Rules

The table below describes the detailed Go/No-Go decision rules for resuming enrollment (GO = Resume enrollment; NG = do not resume enrollment) based on the number of subjects enrolled and number of responses following the interim analysis.

MDS/HL	Number of subjects enrolled at IA			
Number of Responses	10 to 14	15 to 20		
0	NG	NG		
1	NG	NG		
2	GO	NG		
3+	GO	GO		
MM and MLBCL/PD-L1+ NHL	Number of subjects enrolled at IA			
Number of Responses	10 to 11	12 to 15	16 to 18	19 to 20
0 to 3	NG	NG	NG	NG
4	GO	NG	NG	NG
5	GO	GO	NG	NG
6	GO	GO	GO	NG
7	GO	GO	GO	GO

GO = Resume enrollment; NG = do not resume enrollment

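### The pause rule does not count subjects who fail before Week 12 as non-responders, and the resume rule's denominator and 5/16 example conflict with Section 12.8

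*Combined protocol and SAP*

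**What the plan says.** **Pause rule.** Section 8.2.9 (repeated in 8.1.4) sets the timing: "The interim analysis will take place after 10 subjects have reached the Week 12 assessment". For MDS and HL the pause is triggered by "1 or fewer subjects out of the first 10 subjects with a post-baseline (Week 12) assessment/imaging scan" having a response. For MM and for Cohorts 4A and 4B combined it is triggered by "3 or fewer subjects out of the first 10 subjects with a post-baseline (Week 12) imaging scan". Neither section says what happens to a subject who leaves before that assessment.

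**Final analysis.** Section 8.2.4.1 keeps in the FAS a treated subject with a baseline assessment who discontinued for progression or a drug-related AE without any post-baseline assessment. Section 8.2.5.1 counts FAS subjects without response data as non-responders.

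**Resume rule.** During a pause, "response data for the subsequent (Week 24) assessment/imaging scan are reviewed for all subjects already enrolled in the trial". The decision, however, rests on responses "among subjects who are still enrolled in the trial", with an 80% probability threshold and the examples of at least 3/16 (MDS/HL) and at least 5/16 (MM, 4A/4B). Section 12.8, to which the text refers for the detailed rules, describes its grid as "based on the number of subjects enrolled and number of responses following the interim analysis", and its columns are headed "Number of subjects enrolled at IA".

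**The concern.** The look exists to stop enrolment into a cohort where the drug does not work. The subjects most likely to lack a Week 12 assessment are those who did badly. If they are passed over and the next assessed subject takes their place, the 10 counted are a favourable selection. The interim is then more lenient than the plan's own primary analysis, and the operating characteristics in Tables 20 and 21 do not describe it.

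The resume rule has a different problem. Two parts of the plan give two denominators, and one worked example disagrees with the grid it is meant to illustrate. A study team holding one set of data could reach either decision and cite the plan for it.

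**Working it through.** **1. Reproduce the tables.** Inputs: pause limits 1/10 and 3/10 (Section 8.2.9); success limits 6/25 and 12/28 (Section 8.2.7). With X1 the responses among the 10 and X2 those among the remaining 15 or 18:

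- P(pause) = P(X1 ≤ 1 | 10, p) or P(X1 ≤ 3 | 10, p).
- P(pass and succeed) = sum over x above the pause limit of P(X1 = x) × P(X2 ≥ r − x), with r = 6 or 12.

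At the null this gives 0.736 and 0.028 for MDS/HL (printed 0.73 and 0.03), and 0.776 and 0.023 for MM, 4A/4B (printed 0.78 and 0.02). All 15 rows agree within 0.01. The tables therefore assume that each of the 10 responds at the full cohort rate p, with nobody left out.

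**2. Leave early failures out.** Assume that a share d of treated subjects, all non-responders, never has a qualifying assessment. The rate among those counted is then p/(1 − d). The documents give no value for d; 10% to 30% is an assumption.

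| d | Rate counted, null 10% | P(pause), null 10% | P(pause), true 30% | Rate counted, null 25% | P(pause), null 25% | P(pause), true 50% |
|---|---|---|---|---|---|---|
| 0% | 0.100 | 0.736 | 0.149 | 0.250 | 0.776 | 0.172 |
| 10% | 0.111 | 0.693 | 0.104 | 0.278 | 0.708 | 0.096 |
| 20% | 0.125 | 0.639 | 0.064 | 0.313 | 0.616 | 0.038 |
| 30% | 0.143 | 0.571 | 0.032 | 0.357 | 0.494 | 0.008 |

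The look becomes less likely to pause in both directions: it misses more inactive cohorts and wrongly pauses fewer active ones.

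**3. Effect on the final claim.** Keep every treated subject in the final 25 or 28, with the number of early failures before the tenth assessed subject negative binomial. The null probability of passing and succeeding moves from 0.028 to between 0.029 and 0.032 (MDS/HL), and from 0.023 to between 0.025 and 0.028 (MM, 4A/4B). With no interim at all the final rules have error 0.033 and 0.029, so these are ceilings, both under 0.05.

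**4. Which denominator does the Section 12.8 grid use?** The plan states no prior. With a flat prior, P(rate > p0 | x of n) = P(Bin(n + 1, p0) ≤ x). Taking n as the number enrolled at the interim, the grid's boundaries fall at 80%:

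- p0 = 10%: 2/14 gives 0.816 (go); 2/15 gives 0.789 (no-go).
- p0 = 25%: 4/11 gives 0.842 (go) and 4/12 gives 0.794 (no-go); 5/15 gives 0.810 (go) and 5/16 gives 0.765 (no-go); 6/18 gives 0.825 (go) and 6/19 gives 0.786 (no-go).

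The grid thus behaves as a rule on everyone enrolled.

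**5. Consequence of the other denominator.** Take 4 responses, 16 enrolled in MM or 4A/4B, and 11 still enrolled. At n = 16 the grid says no-go (0.574). At n = 11 it says go (0.842). Smaller losses matter too. With 16 enrolled, one departure (n = 15) lowers the requirement from 6 responses to 5, and the unconditional chance of meeting it at a true 25% rises from 0.19 to 0.37. In MDS/HL, two departures (n = 14) lower it from 3 to 2, and the chance at a true 10% rises from 0.21 to 0.49.

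**6. The examples.** The 3/16 example agrees with the grid (0.917). The 5/16 example does not: Section 12.8 gives no-go for 5 responses with 16 to 18 enrolled, and 0.765 is below 0.80. At 6/16 the value is 0.893, which is go.

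**The case against.** **Some early failures may be counted.** The lymphoma flow charts allow the first scan before Week 12 if the subject is clinically progressing. Section 7.1.2.7.4 has MDS, MM and the Q3W lymphoma cohorts assessed before Week 12, and the flow charts ask for an assessment at discontinuation without confirmed progression. This stands as a limit on the size. The plan does not say whether such assessments place a subject among the 10, and a death or exit with no assessment remains uncovered.

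**The loss rate is invented.** True, and for that reason the range is illustrative only.

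**A reader might infer that the resume rule discards everyone who failed.** The documents do not establish this. Section 5.8 says a subject taken off treatment may continue to be monitored in the trial, and Section 7.1.5.3.3 moves progressors into survival follow-up, so many would still be enrolled on an ordinary reading. The operative grid already uses all enrolled. What stands is a contradiction to reconcile. The 4-response example needs five non-responders gone from the trial.

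**A reader might also infer that Tables 20 and 21 are wrong, or overstate the look because of the resume wording.** They are arithmetically right for their own assumption. They cover only the pause and the path without a pause, so the resume wording has no bearing on them.

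**Little is left to protect.** The look is conditional on slow accrual and only pauses enrolment. The plan records enrolment as complete in Cohorts 1, 2 and 3. This reduces the practical weight, but any interim already run still has to be reported on a defined denominator.

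**Conclusion.** The point holds as two separate defects of wording.

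First, the pause rule has no provision for subjects who fail before Week 12 without an assessment, although the final analysis has one. To the extent that they are left out, the null pause probability is below Tables 20 and 21: 0.69 to 0.57 against 0.73, and 0.71 to 0.49 against 0.78. This assumes 10% to 30% early loss, all non-responders and none with a qualifying earlier assessment. Pausing at the design alternative falls as well. It would be tempting to conclude that the efficacy claims are compromised; they are not, because the final error stays at or below 0.033 and 0.029. The cost is further enrolment into an inactive cohort.

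Second, and without any assumption about early loss, the text and Section 12.8 give different resume denominators that can reverse a decision, and the 5/16 example contradicts the grid. The contradiction with the grid is visible on the page; only the quoted probabilities rest on the inferred flat prior.

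**What to change.** In Sections 8.1.4 and 8.2.9:

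- Define the pause set as the first 10 treated subjects, in order of first dose, once each has had a Week 12 assessment or has progressed, died or stopped before it. Count those with no documented response by the interim cut-off as non-responders. Do not count every early discontinuation as a failure: the endpoint is response at any time, so a subject who responded and then stopped must remain a responder. Tables 20 and 21 then hold as printed.
- Replace the still-enrolled condition in the resume rule with all subjects enrolled at the interim, matching Section 12.8.
- Change the MM and 4A/4B example from 5/16 to 6/16, and state the prior behind the 80% criterion.
- For any interim already run, report the result on this denominator in the CSR.

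The cost is SAP wording and possibly one re-tabulation, with no new data. The interim result becomes slightly less favourable.

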### **MM (Cohort 2) and NHL (Cohorts 4A and 4B)**

For the MM (Cohort 2) and combined MLBCL and PD-L1 positive NHL Cohorts 4A and 4B, respectively), if an interim analysis is conducted and 3 or fewer subjects out of the first 10 subjects with a post-baseline (Week 12) imaging scan have a confirmed or unconfirmed primary endpoint response, then enrollment will be paused until response data for the subsequent imaging scan (Week 24) are reviewed for all subjects already enrolled in the trial (including those enrolled who have not reached the first post-baseline scan). Enrollment will be resumed if the observed responses (confirmed or unconfirmed) for the primary endpoint in the respective cohort among subjects who are still enrolled in the trial indicates that the probability of the response for the primary endpoint  $>25\%$  is at least 80% (e.g.,  $\geq 5/16$  confirmed or unconfirmed responses). See Section 12.8 for further details regarding the decision rules for resuming enrollment following the interim analysis. If the required number of responses is observed, enrollment will be resumed in the respective cohort regardless of whether all subjects have had disease assessments through Week 24. [Table 21](#) provides the operating characteristics for this interim analysis rule in MM and MLBCL and PD-L1 Positive NHL Cohorts, respectively.

No interim analysis is planned for subjects with unselected PD-L1 status with relapsed / refractory FL (Cohort 4C) or DLBCL (Cohort 4D).

Table 21 Operating Characteristics of Interim Analysis Rule for MLBCL and PD-L1 Positive NHL subjects (Cohorts 4A and 4B) and MM (Cohort 1)– Pause Enrollment if  $\leq 3/10$  Subjects Achieve an Overall Response (PR or better); Final Analysis with 28 Subjects

True ORR	Probability of Pausing Enrollment	Probability of Passing the IA and Achieving Study Success
25%	0.78	0.02
30%	0.65	0.08
35%	0.51	0.20
40%	0.38	0.37
45%	0.27	0.57
50%	0.17	0.74
55%	0.10	0.86
60%	0.05	0.93

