The primary objectives of the trial are to determine safety, tolerability, and efficacy of pembrolizumab or lenalidomide + pembrolizumab combination in subjects with hematologic malignancies. Secondary objectives include further analysis of various efficacy parameters (time to progression [TTP]/progression-free survival [PFS]/ OS for each respective cohort, as well as an analysis of PD-L1 expression and corresponding efficacy. The pharmacokinetic (PK) properties of pembrolizumab and pembrolizumab when given in combination with lenalidomide, and the relationship of candidate efficacy/resistance biomarkers and anti-tumor activity of pembrolizumab will be investigated as exploratory objectives.

With the initiation of Amendment 013-04, the protocol will be enrolling subjects in the following Cohorts: Cohort 2 (MM), 4A (MLBCL), 4C (FL), and 4D (DLBCL).

With the initiation of Amendment 013-05, subjects will be enrolled in Cohort 5 (DLBCL) to receive lenalidomide + pembrolizumab combination treatment.

This study will be conducted in conformance with Good Clinical Practices.

Due to the unfavorable results (risks outweighed benefits) of KEYNOTE-183 and KEYNOTE-185 in subjects with MM treated with pembrolizumab plus pomalidomide or lenalidomide, subjects enrolled in Cohort 5 who are still receiving combination are to stop combination treatment immediately, complete the discontinuation visit, and move into the long-term safety and survival follow-up per protocol. If clinically benefitting at time of stopping combination therapy, subjects may enter a transition period remaining on single agent lenalidomide or pembrolizumab for up to 90 days from 15-SEP-2017 and then enter long-term survival and safety follow-up.

For Cohort 2, enrollment has been completed and all subjects have previously discontinued study treatment and must transition into long-term safety and survival follow-up. There will be no further enrollment of subjects in this cohort

[figure not shown]
Specific procedures to be performed during the trial, as well as their prescribed times and associated visit windows, are outlined in the Trial Flow Chart - Section 6.0. Details of each procedure are provided in Section 7.0 – Trial Procedures.

An interim analysis will be performed if fewer than 10 subjects are enrolled in a cohort after being open for 6 months from the time that the first subject is treated in the respective cohort. Results will be reviewed by the study team.

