### 8.1.4 Interim Analysis

Unless otherwise indicated, an interim analysis will be performed if fewer than 10 subjects are enrolled in a cohort 6 months after the time that the first subject is treated in the respective cohort. The interim analysis will take place after 10 subjects have reached the Week 12 assessment. Results will be reviewed by the study team.

See Section 12.8 for further details regarding the decision rules for resuming enrollment following the interim analysis.

**Table 16** summarizes the strategy and timing of the potential interim analysis for each cohort.

For the MDS and HL cohorts, if an interim analysis is conducted and 1 or fewer subjects out of the first 10 subjects with a post-baseline (Week 12) assessment/imaging scan have a confirmed or unconfirmed primary endpoint response (OR or CR respectively), then enrollment will be paused until response data for the subsequent (Week 24) assessment/imaging scan are reviewed for all subjects already enrolled in the trial (including those enrolled who have not reached the first post-baseline assessment/imaging scan). Enrollment will be resumed if the observed responses (confirmed or unconfirmed) for the primary endpoint in the respective cohort among subjects who are still enrolled in the trial indicates that the probability of the response for the primary endpoint  $>10\%$  is at least 80% (e.g.,  $\geq 3/16$  confirmed or unconfirmed responses). See Section 12.8 for further details regarding the decision rules for resuming enrollment following the interim analysis.

For the MM and NHL Cohorts 4A and 4B combined, if an interim analysis is conducted and 3 or fewer subjects out of the first 10 subjects with a post-baseline (Week 12) imaging scan have a confirmed or unconfirmed primary endpoint response, then enrollment will be paused until response data for the subsequent imaging scan (Week 24) are reviewed for all subjects already enrolled in the trial (including those enrolled who have not reached the first post-baseline scan). Enrollment will be resumed if the observed responses (confirmed or unconfirmed) for the primary endpoint in the respective cohort among subjects who are still enrolled in the trial indicates that the probability of the response for the primary endpoint  $>25\%$  is at least 80% (e.g.,  $\geq 5/16$  confirmed or unconfirmed responses). See Section 12.8 for further details regarding the decision rules for resuming enrollment following the interim analysis.

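### The 5/16 example for resuming enrollment in MM and NHL 4A/4B (Sections 8.1.4 and 8.2.9) is a no-go in the Section 12.8 table that both sections cite

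*Combined protocol and SAP*

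**What the plan says.** Section 8.2.9 provides for a look in slowly accruing cohorts: "an interim analysis will be performed if fewer than 10 subjects are enrolled in a cohort 6 months after the time" the first subject is treated. The look itself waits until 10 subjects have reached the Week 12 assessment. For MM (Cohort 2) and for NHL Cohorts 4A and 4B combined, 3 or fewer responders among the first 10 pauses enrollment. Enrollment resumes when the later data put the probability of a response rate above 25% at 80% or more; in the document's words, this probability "is at least 80% (e.g., $\geq 5/16$ confirmed or unconfirmed responses"). Section 8.1.4 gives the same rule and the same example.

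Both sections then point to the appendix: "See Section 12.8 for further details regarding the decision rules for resuming enrollment following the interim analysis". Section 12.8 opens with "The table below describes the detailed Go/No-Go decision rules for resuming enrollment". Its MM and MLBCL/PD-L1+ NHL block reads as follows:

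| Enrolled at the look | Largest no-go count | Smallest go count |
|---|---|---|
| 10 to 11 | 3 | 4 |
| 12 to 15 | 4 | 5 |
| 16 to 18 | 5 | 6 |
| 19 to 20 | 6 | 7 |

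The MDS/HL paragraph of Section 8.2.9 has a parallel example against a 10% reference rate: "e.g., $\geq 3/16$ confirmed or unconfirmed responses". Section 12.8 gives go for 3 or more responses with 15 to 20 enrolled, so that example agrees with its table.

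**The concern.** With 16 subjects enrolled and 5 responses, the worked example says resume and the table it cites says do not resume. This is the only numerical threshold for resuming that the SAP body gives for these cohorts, and it appears twice. The pause exists to avoid enrolling further patients into a cohort that looks inactive, so a looser number weakens it in exactly that situation. The documents do not say whether an interim analysis took place. If one did, a reader working from the SAP text alone could not tell which threshold was applied.

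**Working it through.** **Step 1: direct comparison, no model needed.** Sections 8.1.4 and 8.2.9 treat 5/16 as meeting the resume rule. In Section 12.8, 16 enrolled falls in the 16 to 18 column, where 5 is a no-go and 6 is a go.

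**Step 2: which of the two follows the stated 80% criterion.** No prior is given, so I assume Beta(1,1). After x responses in n subjects the posterior is Beta(1+x, 1+n−x), and the rule is P(p > p0) ≥ 0.80 with p0 = 0.25 (MM/NHL) or 0.10 (MDS/HL).

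| Result | p0 | P(p > p0) | 80% rule | Section 12.8 |
|---|---|---|---|---|
| 4/11 | 0.25 | 0.842 | go | go |
| 4/12 | 0.25 | 0.794 | no-go | no-go |
| 5/15 | 0.25 | 0.810 | go | go |
| **5/16** | 0.25 | **0.765** | **no-go** | **no-go** |
| 6/16 | 0.25 | 0.893 | go | go |
| 6/18 | 0.25 | 0.825 | go | go |
| 6/19 | 0.25 | 0.786 | no-go | no-go |
| 7/19 | 0.25 | 0.898 | go | go |
| 2/14 | 0.10 | 0.816 | go | go |
| 2/15 | 0.10 | 0.789 | no-go | no-go |
| 3/16 | 0.10 | 0.917 | go | go |

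The smallest x with posterior probability at least 0.80, taken for each n from 10 to 20, matches Section 12.8 in 11 of 11 cases for MM/NHL and 11 of 11 for MDS/HL. The table therefore follows the 80% rule and the 5/16 example does not.

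**Step 3: effect on pausing and resuming.** Assume 16 enrolled and no change of response status among the first 10. The chance of pausing and then reaching threshold k is the sum over x = 0..3 of Bin(x; 10, p) × P(Bin(6, p) ≥ k−x).

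| True ORR | k = 5 | k = 6 | Difference (exactly 5/16) |
|---|---|---|---|
| 25% | 0.172 | 0.054 | 0.118 |
| 50% | 0.137 | 0.093 | 0.044 |

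**Step 4: effect on the final 12/28 test (Section 8.2.7, MM).** Overall success is the sum of two terms:

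- not paused: sum over x = 4..10 of Bin(x; 10, p) × P(Bin(18, p) ≥ 12−x);
- paused, then resumed: sum over x = 0..3 and y = 0..6 with x+y ≥ k of Bin(x; 10, p) × Bin(y; 6, p) × P(Bin(12, p) ≥ 12−x−y).

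The first term reproduces Table 21: 0.0228 at 25% (printed 0.02) and 0.738 at 50% (printed 0.74).

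| True ORR | k = 5 | k = 6 | Single stage, P(Bin(28, p) ≥ 12) |
|---|---|---|---|
| 25% | 0.0288 | 0.0271 | 0.0294 |
| 50% | 0.822 | 0.805 | 0.828 |

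Tables 20 and 21 count as successes only cohorts that were not paused, so they are unaffected.

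**Step 5: how often the case arises.** The look waits 12 weeks after the tenth subject starts. At an assumed 9 or 10 subjects per 26 weeks, the expected further enrollment is 12×9/26 = 4.15 or 12×10/26 = 4.62, so about 14 to 15 would be enrolled at the look. As a Poisson count, 16 or more enrolled has probability 0.24 to 0.32, and exactly 16 has 0.112 to 0.133. The example bites only at exactly 16 enrolled and exactly 5 responses:

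- true ORR 25%: 0.118×0.112 = 0.013 to 0.118×0.133 = 0.016;
- true ORR 50%: 0.044×0.112 = 0.005 to 0.044×0.133 = 0.006.

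Both are conditional on a look taking place.

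**The case against.** The strongest case is that this is a wrong illustration beside a correct operative table. The figure is introduced as an example, the next sentence defers to Section 12.8, and a careful reader will use the table without needing a prior. The correction is also unlikely to change any decision now. Section 2.1 states "For Cohort 2, enrollment has been completed and all subjects have previously discontinued study treatment", and Cohort 4B is absent from its list for Amendment 04: "the protocol will be enrolling subjects in the following Cohorts: Cohort 2 (MM), 4A (MLBCL), 4C (FL), and 4D (DLBCL"). The rule governs enrollment only and leaves the final success criteria alone. These points stand, and they limit the severity. They do not make the printed number right, since an example of meeting a criterion has to meet it.

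Three attempts to rescue the example fail:

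- **Another prior.** Under Beta(2,2), 5/16 gives 0.825 and passes. But the same prior gives 0.852 for 4/12, which Section 12.8 makes a no-go, so it does not generate the table. Jeffreys gives 0.729 for 5/16.
- **A binomial tail.** P(X ≤ 5 | n = 16, p = 0.25) = 0.810 exceeds 80%. It is not the probability that the rate exceeds 25%, and as a rule it departs from Section 12.8 at n = 12, 16 and 19 for MM/NHL and at n = 15 for MDS/HL.
- **Different denominators.** The text counts subjects still enrolled and the table counts subjects enrolled at the look. If 16 are still enrolled, at least 16 were enrolled, and 5 responses is a no-go in every column from 16 up.

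The request for a CSR statement is fairly called conditional: it applies only if an interim analysis was done in these cohorts.

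**Conclusion.** The concern holds. The example in Sections 8.1.4 and 8.2.9 contradicts Section 12.8, and this rests on the text alone. That the example rather than the table is wrong rests on an inferred Beta(1,1) prior, supported by its match to all 22 cut-offs.

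The consequence is limited. At a true rate of 25% with 16 enrolled, the looser threshold raises the chance of pausing and then resuming from 0.054 to 0.172, but it moves overall success only from 0.0271 to 0.0288, below the single-stage 0.0294. The exact conflict would arise in about 1.3% to 1.6% of looks at that rate, under the assumed accrual of 9 to 10 subjects per 26 weeks. It should be corrected because a decision threshold is misstated twice and the repair is nearly free.

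**What to change.** In Sections 8.1.4 and 8.2.9, replace the 5/16 example for MM and NHL 4A/4B with 6/16 (or 5/15), and add a clause saying that the Section 12.8 table governs. Optionally name the prior behind the 80% criterion; Beta(1,1) fits, and the sponsor should confirm it. If an interim analysis was carried out in Cohort 2 or in Cohorts 4A/4B, state in the CSR which threshold was applied. The cost is one number and one clause in two sections, plus possibly one CSR sentence, with no further data or patients.
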